8.2 SAFETY

The assessment of overall safety consists in recording and evaluating all adverse events, haematological and chemical parameters (see [Section 8.1.4](#)), and vital signs. The following adverse events are of particular interest in this study:

- Nausea, vomiting, abdominal pain, bloating, thirst, dizziness, sleep disturbance, hypotension
- Acute disruption of electrolyte homeostasis
- Complications of colonoscopy: colonic perforation, bleeding, cardiovascular complications, explosion

8.3 ADVERSE EVENTS AND SERIOUS ADVERSE EVENTS

8.3.1 DEFINITION OF ADVERSE EVENTS (AE)

An adverse event can be defined as any untoward medical occurrence in a subject to whom a medicinal product is administered and which does not necessarily have a causal relationship with this treatment. An AE can be any unfavourable and unintended sign (including an abnormal laboratory finding), symptom or disease temporally associated with the use of a medicinal product, whether or not considered related to the medicinal product.

8.3.2 DEFINITION OF SERIOUS ADVERSE EVENTS (SAE)

An AE or suspected adverse reaction is considered "serious" if, in the view of either the investigator or sponsor, it results in any of the following outcomes: death, a life-threatening adverse event, inpatient hospitalization or prolongation of existing hospitalization, a persistent or significant incapacity or substantial disruption of the ability to conduct normal life functions, or a congenital anomaly/birth defect. Important medical events that may not result in death, be life-threatening, or require hospitalization may be considered serious when, based upon medical judgment, they may jeopardize the participant and may require medical or surgical intervention to prevent one of the outcomes listed in this definition.

8.3.3 CLASSIFICATION OF AN ADVERSE EVENT

8.3.3.1 SEVERITY OF EVENT

The following guidelines will be used to describe severity.

- Mild – Events require minimal or no treatment and do not interfere with the participant's daily activities.
- Moderate – Events result in a low level of inconvenience or concern with the therapeutic measures. Moderate events may cause some interference with functioning.
- Severe – Events interrupt a participant's usual daily activity and may require systemic drug therapy or other treatment. Severe events are usually potentially life-threatening or incapacitating. Of note, the term "severe" does not necessarily equate to "serious".

8.3.3.2 RELATIONSHIP TO STUDY INTERVENTION

All AEs must have their relationship to study intervention assessed by the clinician who examines and evaluates the participant based on temporal relationship and his/her clinical judgment. Investigators are to judge the causal relationship of the event with the study intervention as "suspected", "unsuspected" or "unknown".

8.3.3.3 EXPECTEDNESS

The Sponsor will be responsible for determining whether an AE is expected or unexpected. An AE will be considered unexpected if the nature, severity, or frequency of the event is not consistent with the reference safety information.

8.3.4 TIME PERIOD AND FREQUENCY FOR EVENT ASSESSMENT AND FOLLOW-UP

The occurrence of an AE or SAE may come to the attention of study personnel during study visits and interviews of a study participant presenting for medical care, or upon review by a study monitor.

All AEs including local and systemic reactions will be captured on the appropriate case report form (eCRF). Information to be collected includes event description (a diagnosis and not symptoms should be provided, if possible), time of onset, clinician's assessment of severity, relationship to study drugs, and time of resolution/stabilization of the event. All AEs occurring while on study must be documented appropriately regardless of relationship. All AEs will be followed to adequate resolution.

Any medical condition that is present at the time that the participant is screened will be considered as baseline and not reported as an AE. However, if the study participant's condition deteriorates at any time during the study, it will be recorded as an AE.

Changes in the severity of an AE will be documented to allow an assessment of the duration of the event at each level of severity to be performed. AEs characterized as intermittent require documentation of onset and duration of each episode.

The Investigator will record all reportable events with onset dates occurring any time after informed consent is obtained up to and including the day of colonoscopy. Events will be followed for outcome information until resolution or stabilization, except for those events deemed to be chronic by the Investigator, such as cancer. Lesions detected during colonoscopy (polyps, adenomas, cancer, diverticulosis, hernia, etc.) are not to be considered as AEs.

8.3.5 NON-SERIOUS ADVERSE EVENT REPORTING

All identified non-serious AEs (related and unrelated) must be recorded and described on the eCRF.

8.3.6 SERIOUS ADVERSE EVENT REPORTING

Every SAE, regardless of suspected causality, occurring after the subject has provided informed consent up to and including the day of colonoscopy, must be reported to the sponsor immediately but not later than 24 hours after site awareness.

Any SAE experienced after this period should only be reported to the sponsor if the Investigator suspects a causal relationship to the study treatment. Recurrent episodes, complications, or progression of the initial SAE must be reported as follow-up to the original episode within 24 hours of the Investigator receiving the follow-up information.

Information about all SAEs will be recorded using the e-safety tool of the eCRF. In case of technical difficulties, SAE notification can be carried out using a paper SAE form and by contacting OPIS, a contract research organization (CRO), via email at [contact] or by fax using the following number: [name].

All SAEs will be followed until satisfactory resolution or until the site Investigator deems the event to be chronic. Other supporting documentation of the event may be requested by the study sponsor and should be provided as soon as possible. The study sponsor will be responsible for notifying Health Authorities of any unexpected fatal or life-threatening suspected adverse reaction as soon as possible, but in no case later than 7 calendar days after the sponsor's initial receipt of the information.

8.3.7 REPORTING OF PREGNANCY

Pregnant women will not be permitted to participate in this study. A negative pregnancy test will be required to enter the study. The Investigator shall report all pregnancy exposures occurring in a female patient within 24 hours to the sponsor using the e-pregnancy tool of the eCRF. In case of technical difficulties, pregnancy notification can be carried out using a paper pregnancy form and by contacting the CRO via email at [contact] or by fax using the following number: [name]. The Investigator should counsel the subject and discuss the risks of continuing with the pregnancy and the possible effects on the foetus potentially induced by participation in the study. Monitoring of the subject should continue until conclusion of the pregnancy.

9 STATISTICAL CONSIDERATIONS

9.1 SAMPLE SIZE DETERMINATION

The total number of patients to be enrolled is approximately 846; 150 patients (50 in each mannitol dose group) for phase II dose finding, and 696 patients (348 in each treatment group) for the phase III non-inferiority study. The population for phase III will not include the patients who participated in phase II.

Phase II - Dose finding

The sample size is based on the precision of the estimate within each treatment group, i.e. the 95% confidence interval of the proportion of patients in each treatment group with adequate bowel cleansing (BBPS total score ≥ 6 , with BBPS ≥ 2 for each segment).

The table below shows the precision of the estimate for different rates of adequate bowel cleansing with a sample size of 50 patients.

Rates of adequate bowel cleansing (%)	Estimate Precision (%) (i.e. 95% CI*)
75	± 12
80	± 11
85	± 10

* Confidence interval estimated through normal approximation of binomial distribution without continuity correction.

Phase II - Pharmacokinetic sub-study

The expected sample size (10 patients in each dose group) is based on feasibility criteria.

Phase III - non-inferiority

The sample size is based on the proportion of patients with adequate bowel cleansing (BBPS total score ≥ 6 , with BBPS ≥ 2 for each segment). When the sample size in each group is 313, a two-group large-sample normal approximation test of difference of proportions with a one-sided 0.025 significance level will have 80% power to reject the null hypothesis that the test preparation is inferior to the standard preparation in favour of the alternative hypothesis that the test proportion is not inferior to the standard preparation (the difference in success proportions, $\pi_T - \pi_S$, is -0.08 or farther from zero in the same direction), assuming that the expected difference in success proportions is 0 and the proportion of successes in the standard group is 0.85 (the success rate for Moviprep® as reported in Bisschops R. et al., 2019, Choi et al., 2018 and Kwon et al., 2016 varies from 85% to 89%).

A proportion of patients with adequate bowel cleansing 8% lower than the expected 85% for gold standard Moviprep® would give a 77% success rate for mannitol, which falls within the 70-88.5% range reported for PEG-ASC (Repici et al., 2012; Choi et al., 2018; Hassan et al., 2013).

Sample size for two-group test of equivalence in proportions (large equal n's)

Test significance level, α (one-sided)	0.025
Standard proportion, π_S	0.85
Equivalence limit difference, $\pi_T - \pi_S, \Delta_0$	-0.08
Test expected proportion, π_T	0.85
Expected difference, $\pi_T - \pi_S, \Delta_1$	0
Power (%)	80
N per group	313

Sample size was computed based on normal approximation of binomial distribution without continuity correction

The non-inferiority margin $\pi_T - \pi_S = -0.08$ corresponds to a relative risk $\pi_T/\pi_S = 0.906$. Should the proportion of successes in the standard group be lower than 0.85, the non-inferiority margin will be adjusted in order to have a relative risk of at least 0.906 (e.g. if the proportion of successes observed in the standard group is 0.80, the non-inferiority margin $\pi_T - \pi_S$ will be set equal to = -0.075, corresponding to a relative risk equal to 0.906).

The total sample size (626) is adjusted to 696 patients (348 in each treatment group) considering an expected rate of dropouts and major protocol deviations of about 10% (using Freedman's formula (*Control Clin Trials*, 1990): $n' = 100*n/(100-x)$, where x is the expected percent dropout rate).

The correctness of the assumptions used to compute the sample size for phase III of the study will be re-evaluated at the end of phase II and, if needed, the sample size will be re-estimated.

9.2 RANDOMIZATION

At Visit 3, all eligible subjects will be randomized via eCRF to one of the treatment groups according to the study phase. The Investigator or his/her delegate will confirm that the subject has fulfilled all the inclusion/exclusion criteria in the eCRF. The eCRF will assign a randomization number to the subject, which will be used to link the subject to the treatment and will specify a unique medication number for the package of study treatment to be dispensed to the subject. The subject's randomization number will not be shown in the eCRF: only the medication number will be made available.

For each phase of the study a stratified subject randomization list will be produced in balanced blocks through a validated SAS program.

Phase II – dose finding: the randomization will be stratified by centre and by the presence of constipation (yes/no), defined as the recurrent use of laxatives or Bristol Stool Form Scale (BSFS) < 3 in the two weeks before randomisation.

Phase III – non-inferiority: the randomization will be stratified by centre.

9.3 POPULATIONS FOR ANALYSES

The following populations will be used for the statistical analyses:

- Safety set: all patients who take the study preparation, even only partially. Patients will be analysed according to the study drug dose actually received.
- Modified Safety set: all patients who take the study preparation, even only partially, and who do not meet significant protocol violations that regard inclusion/exclusion criteria. Patients will be analysed according to the study drug dose actually received.
- PK population (only for the pharmacokinetic sub-study): all randomized patients who complete the mannitol treatment and have at least one PK assessment, regardless of the outcome of colonoscopy. Patients will be analysed according to the study drug dose actually received.
- Full Analysis Set (FAS): all randomized patients who take the study preparation, even only partially, undergo the colonoscopy, and have a BBPS available for at least one colon segment after standard washing and air insufflation for luminal distension. According to the Intention to Treat (ITT) principle, patients will be analysed according to the study drug dose assigned at randomization.
- Per protocol (PP): all randomized patients who meet the following criteria:
 - Treatment with the study drug completed.
 - Colonoscopy completed adequately in absence of pathological obstruction that prevents reaching the right colon, including the cecum (i.e. endoscope does not find obstacles other than faecal material) and without acute deterioration of general conditions causing procedure suspension.
 - Bowel cleansing assessment and gas measurement are available for all colon segments after standard washing and air insufflation for luminal distension.
 - No significant protocol violations that regard inclusion/exclusion criteria or that can condition evaluations.

Patients will be analysed according to the study drug dose actually received.

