Statistical considerations	
Populations for analyses
 
The following populations will be used for the statistical analyses:
 
 • Safety set: all patients who take the study preparation, even only partially. • Modified Safety set: all patients who take the study preparation, even only partially, and who do not meet significant protocol violations that regard inclusion/exclusion criteria. • PK population (only for the pharmacokinetic sub-study): all randomized patients who complete the mannitol treatment and have at least one PK assessment, regardless of the outcome of colonoscopy.

	
• Full Analysis Set (FAS): all randomized patients who take the study preparation, even only partially, undergo colonoscopy, and have a BBPS available for at least one colon segment after standard washing and air insufflation for luminal distension.• Per protocol (PP): all randomized patients who meet the following criteria:
◦ Treatment with the study drug completed.◦ Colonoscopy completed adequately in the absence of pathological obstruction that prevents reaching the right colon, including cecum, (i.e. endoscope does not find obstacles other than faecal material), and without acute deterioration of general conditions causing the suspension of the procedure.◦ BBPS and H₂ and CH₄ measurement are available for all colon segments after standard washing and air insufflation for luminal distension.◦ No significant protocol violations that regard inclusion/exclusion criteria or that can impact evaluations.

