	
Analysis of primary variables
 
Phase II – dose finding
 
The identification of the effective and safe mannitol dose to be used in the non-inferiority assessment will be performed at the end of dose finding based on the following criteria:
 
• 75% or greater rate of adequate bowel cleansing defined as BBPS total score ≥ 6, with a score for each of the three colon segments (right; transverse, including flexures; and left, including sigmoid and rectum) ≥ 2 during colonoscopy after standard washing and air insufflation for luminal distension.• Rate of patients in safe conditions defined as the absence of potentially dangerous levels of H₂ and CH₄.• Clinical judgment based on the caecal intubation rate, the incidence of clinically significant adverse events, treatment adherence and acceptability. 
Descriptive statistics and 95% CI of the proportion of patients with adequate bowel cleansing will be provided for each dose. Logistic regression models will be applied to assess the influence of the two stratification factors and other potential prognostic factors on dose response. No between-group comparisons will be performed. The decision will be made on the basis of descriptive statistics and 95% CIs.
 
Phase III – non-inferiority
 
The proportion of patients with adequate bowel cleansing (BBPS total score ≥ 6, score ≥ 2 for each segment) will be calculated to evaluate the non-inferiority of the test drug vs the standard drug.
 
Non-inferiority will be assessed by computing the two-tailed 95% confidence interval (CI) of the difference between the two proportions $\pi_T - \pi_S$. Non-inferiority is met if the 95% CI does not cross the predefined non-inferiority margin $\Delta = -0.08$ and lies entirely to the right of the margin. Furthermore, if the 95% CI lies entirely to the right of 0, it will be possible to claim for the superiority of the mannitol solution (Pearlitol® PF).
 
The non-inferiority margin $\pi_T - \pi_S = -0.08$ corresponds to a relative risk $\pi_T/\pi_S = 0.906$ when the proportion of successes in the standard group is 0.85. Should the proportion of successes in the standard group be lower than 0.85, the non-inferiority margin will be adjusted in order to have a relative risk of at least 0.906.
 
The analysis will be performed on both the FAS and PP populations. Results from the two populations will have equal importance.

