7.2 PARTICIPANT DISCONTINUATION/WITHDRAWAL FROM THE STUDY

Participants are free to withdraw from participation in the study at any time upon request. An Investigator may discontinue or withdraw a participant from the study for the following reasons:

- Pregnancy.
- If any AE or other medical condition or situation occurs such that continued participation in the study would not be in the best interest of the participant.
- If the participant meets an exclusion criterion (either newly developed or not previously recognized) that precludes further study participation.

The reason for participant discontinuation or withdrawal from the study will be recorded on the eCRF.

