Descriptive statistics and Wald 95% CIs of the following adherence and acceptability variables will be provided for each dose:

- Adherence
- NRS score for ease of use and taste
- Willingness to reuse the preparation

Phase II - Pharmacokinetic sub-study

The pharmacokinetic parameters (C_{max} , t_{max} , AUC_{0-t} , $t_{1/2}$) of each dose will be analysed descriptively on the PK population.

Phase III - Non-inferiority

Primary efficacy analysis

The proportion of patients with adequate bowel cleansing (BBPS total score ≥ 6 , score ≥ 2 for each segment) during colonoscopy after standard washing and air insufflation for luminal distension will be calculated to evaluate the non-inferiority of the test drug vs the standard drug.

Non-inferiority will be assessed by computing the two-tailed Wald 95% confidence interval (CI) of the difference between the two proportions $\pi_T - \pi_S$. Non-inferiority is met if the 95% CI does not cross the predefined non-inferiority margin $\Delta = -0.08$ and lies entirely to the right of the margin (i.e. non-inferiority will be demonstrated if the lower bound of the two-sided 95% CI of the difference is > -0.08).

The non-inferiority margin $\pi_T - \pi_S = -0.08$ corresponds to a relative risk $\pi_T/\pi_S = 0.906$ when the proportion of successes in the standard group is 0.85. Should the proportion of successes in the standard group be lower than 0.85, the non-inferiority margin will be adjusted in order to have a relative risk of at least 0.906 (e.g. if the proportion of successes observed in the standard group is 0.80, the non-inferiority margin $\pi_T - \pi_S$ will be set equal to $= -0.075$, corresponding to a relative risk equal to 0.906).

If the 95% CI of the difference lies completely to the right of 0, the test treatment can be considered superior to the standard treatment at a 5% significance level.

The Wald method for non-inferiority of proportions will be applied (*Dann RS, 2008*).

The analysis will be performed on both the FAS and PP populations. Results from both populations will have equal importance.

Secondary efficacy analyses

The analysis of secondary variables will be performed on the FAS. No between-group inferential analysis will be performed. Descriptive statistics and 95% CIs of the between-group differences will be applied on the following variables:

- Number, appearance, size, location and histological classification of neoplastic and inflammatory colorectal lesions detected

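### Both Phase III primary sets omit treated patients with no scored BBPS segment, and no efficacy analysis of all treated patients is planned as a check

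*Combined protocol and SAP*

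**What the plan says.** Protocol section 9.3 admits to the FAS randomised patients who took at least some preparation, "undergo the colonoscopy, and have a BBPS available for at least one colon segment after standard washing and air insufflation". The synopsis (1.1) has the same condition: "undergo colonoscopy, and have a BBPS available for at least one colon segment after standard washing and air insufflation for luminal distension". Section 9.3 then adds: "According to the Intention to Treat (ITT) principle, patients will be analysed according to the study drug dose assigned at randomization". That sentence settles the arm in which a patient is counted, not who is counted.

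The PP set requires completed treatment, an adequately completed colonoscopy and, among other conditions, "Bowel cleansing assessment and gas measurement are available for all colon segments after standard washing and air insufflation for luminal distension".

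The Phase III primary analysis (9.4.1) is run on these two sets: "Results from both populations will have equal importance". The synopsis agrees: "Results from the two populations will have equal importance". Secondary efficacy and the adherence and acceptability variables use the FAS. The Safety set holds every treated patient, but 9.4.2 uses it and the modified Safety set only for safety summaries.

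Sections 9.3 to 9.4.3 contain no rule for a missing BBPS, no statement that a cancelled or unscored examination counts as a failure, and no efficacy analysis of all treated patients.

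**The concern.** The preparation is taken before the examination, so a patient can be exposed and never scored. Section 7.2 is a general withdrawal clause, but it allows withdrawal after intake, for example "If any AE or other medical condition or situation occurs such that continued participation in the study would not be in the best interest". Section 7.3 covers patients who do not appear.

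Some of these patients will be unscored because the preparation was not tolerated or did not work. For a cleansing endpoint that is a poor outcome, yet it leaves the denominator. If this happens more often on mannitol, the FAS difference moves towards zero and non-inferiority becomes easier to declare. If it happens more often on Moviprep, the opposite holds. Running FAS and PP side by side is meant to show whether exclusions matter, but it cannot show the effect of an exclusion that both sets share.

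**Working it through.** **Inputs.** From 9.1 and 9.4.1: one-sided alpha 0.025, power 80%, success 0.85 in both arms, margin −0.08, two-sided 95% Wald interval, 348 per arm. From 9.4.1, on the margin: "Should the proportion of successes in the standard group be lower than 0.85, the non-inferiority margin will be adjusted" so that the relative risk is at least 0.906. The loss rates are assumptions, because the documents give none.

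**The plan's own figure.** n = (1.960 + 0.842)² × 2 × 0.85 × 0.15 / 0.08² = 312.7, so 313 per arm. 626 / 0.90 = 695.6, so 696, or 348 per arm. The sample size reproduces and is not in dispute.

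**Who is in which set.**

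| Treated patient | FAS | PP | All-treated efficacy analysis |
|---|---|---|---|
| Stool-blocked segment scored 0 (8.1.1) | in, not adequate | in, if the other conditions hold | none planned |
| One or two segments scored | in | out | none planned |
| No segment scored | out | out | none planned |

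Only the last row is the gap.

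**Decision rule tested.** Lower bound = (p_T − p_S) − 1.96 × √[p_T(1−p_T)/n_T + p_S(1−p_S)/n_S]. Non-inferiority is declared if this exceeds −m, where m = 0.08 when the observed Moviprep rate is at least 0.85, and otherwise 0.094 × that rate (1 − 0.906 = 0.094).

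**Error if failures go unscored.** Set the truth among all treated patients at the margin: 0.77 against 0.85. Let shares e_T and e_S of each arm be failures with no score. The FAS rates become 0.77/(1−e_T) and 0.85/(1−e_S). At 3%/1%, for example, 0.77/0.97 − 0.85/0.99 = 0.7938 − 0.8586 = −0.065, not −0.08. With 2,000,000 simulated trials per row:

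| Unscored, mannitol/Moviprep | FAS difference | False non-inferiority, adjusted margin | Fixed −0.08 |
|---|---|---|---|
| 0% / 0% | −0.080 | 2.1% | 2.5% |
| 1% / 1% | −0.081 | 2.1% | 2.4% |
| 1% / 0% | −0.072 | 4.0% | 4.6% |
| 2% / 1% | −0.073 | 4.0% | 4.4% |
| 3% / 1% | −0.065 | 7.2% | 7.8% |
| 0% / 1% | −0.089 | 1.0% | 1.2% |

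**How many patients change a result.** Unscored patients are added back as failures.

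| Starting FAS result, mannitol vs Moviprep | Lower bound | Added back | New lower bound |
|---|---|---|---|
| 284/340 vs 289/340 | −0.069, pass | 5 on mannitol: 284/345 | −0.082, fail |
| 284/340 vs 289/340 | −0.069, pass | 5 in each arm: 284/345 vs 289/345 | −0.070 against −0.079, pass |
| 278/340 vs 289/340 | −0.088, fail | 5 on Moviprep: 289/345 | −0.077 against −0.079, pass |
| 289/340 vs 289/340 | −0.054, pass | 10 on mannitol: 289/350 | −0.079, pass |
| 289/340 vs 289/340 | −0.054, pass | 11 on mannitol: 289/351 | −0.082, fail |

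The last two rows show scale only, since 350 and 351 exceed the planned 348. Within 348 treated per arm the count is similar: 287/338 against 296/348 passes on the FAS (−0.055), and adding back the 10 unscored mannitol patients gives 287/348 against 296/348, lower bound −0.081, a fail.

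**The case against.** The strongest reply is that few patients are affected. An endoscopist who meets stool that cannot be cleared can score the segment 0, so most failed preparations that reach endoscopy stay in the FAS and count against the arm. A patient with one or two scored segments is also in the FAS and cannot meet an endpoint that requires all three. This stands, and it limits the point to examinations cancelled or stopped before any score.

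The size is also assumed. Section 2.1 cites aborted examinations at 1% and 6.5% in one study and 6.9% and 21.2% in another. These are not rates of unscored examinations, because an aborted examination with one scored segment remains in the FAS. The error table also treats every unscored patient as a failure, while some cancellations will have nothing to do with cleansing. Equal percentage losses do not inflate the error. The five-patient reversals start close to the margin. All of this stands.

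A reader might infer that the definitions favour mannitol. The documents do not support that. Section 2.2.2 expects better compliance with mannitol. The higher abort rate with non-split dosing in 2.1 compares PEG regimens and says nothing direct about mannitol. A reader might also infer that 7.2 shows the plan expects unscored failures, but it is a general clause and does not mention them.

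None of this answers the gap itself: no planned analysis would show whether the exclusion mattered.

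**Conclusion.** The point holds in a limited form. The text leaves no doubt that a treated patient with no scored segment is outside both Phase III primary sets and that no efficacy analysis of all treated patients is planned. How many such patients there will be, and in which arm, cannot be known from the documents.

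Under the stated assumptions (truth at 77% against 85%, 348 per arm, adjusted margin, all unscored patients failures), false non-inferiority stays at 2.1% when 1% is lost in each arm. It rises to about 4% with an excess of one percentage point on mannitol and about 7% with two, and falls to about 1% when the 1% is lost on Moviprep only. Close to the margin, five losses in one arm can reverse the conclusion either way. From equal observed rates near 85% it takes about 10 or 11.

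A reader might conclude that the primary FAS must be redefined. The documents do not require that. It would turn the endpoint into a composite of cleansing and reaching a scored examination, and would cost power. A sensitivity analysis answers the question without either effect. This is worth fixing before database lock, because a rule chosen after unblinding would be post hoc.

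**What to change.** Leave the FAS and PP primary analyses as they are. In 9.3 and 9.4.1:

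1. Add one prespecified sensitivity analysis of the Phase III primary endpoint on all randomised patients who took any study preparation, analysed as randomised. Use the same Wald interval and margin rule. Count every patient without three segment scores as not adequate.
2. Add a second version that leaves out patients whose missing scores have a documented cause unrelated to the preparation, classified blind to arm before database lock.
3. Report the patients excluded from the FAS and from the PP set, with reasons, by arm.

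The cost is some extra analysis, a short blinded review and one eCRF field for why an examination was cancelled or not scored. Section 7.2 already records reasons for discontinuation or withdrawal, but not this. The primary analysis loses no power and the sample size does not change.
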